A previous retrospective chart review of patients at the UNM Urogynecology office showed that patients travel 42.4 miles on average (SD +/- 91.5 miles) for their appointments. [16] In addition, Albuquerque is the only city in New Mexico with board certified Urogynecologists. Patients carry a significant burden of cost and time required for routine postoperative visits.

2.3. Provide the scientific or scholarly background for, rationale for, and significance of the research based on the existing literature and how will it add to existing knowledge.

Retrospective studies have evaluated telephone evaluation in place of traditional outpatient visits in the pediatric and adult surgery literature including general surgery, urology, and orthopedic surgery.[4-10] Although validated measures were not used, global satisfaction scores were high, patients' indirect costs reduced, and, on the side of the providers, increased time available for new patients or other follow-up visits was created. Importantly, surgical outcomes were similar. These factors—outcomes and satisfaction improvement, cost reduction, clinical efficiency—have the potential to improve healthcare value in the postoperative setting and overall achieve the National Quality Strategy aims.

Telephone follow-up for postoperative care has not been evaluated using a randomized controlled study design with validated measures and has not been rigorously evaluated in the Urogynecologic literature. The British medical system has adopted the use of telephone follow-up by a clinical nurse after Urogynecologic procedures. One retrospective study using the British Society of Urogynaecology database showed 90% of women who underwent a midurethral sling received telephone follow-up and did not require an outpatient visit.[17] Using this same database, a retrospective observational study showed a trend toward self-directed care, in which patients self-present if complications occur.[18] These results along with the retrospective studies from other surgical

Outpatient Visits versus Telephone Interviews for Postoperative Care: A Randomized Controlled Trial (OPTIONS)

fields provide the rationale behind a randomized controlled study for postoperative telephone follow-up after surgery for pelvic floor disorders.

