Patients will be scheduled to receive a telephone call from qualified medical staff from the Urogynecology office at 1-2 weeks, 6 weeks (+/-2 weeks), and 3 months (+/-3 weeks). A scripted interview (See forms: *1-2 Week Interview, 6 Week Interview, and 3 Month Interview*) will be conducted to evaluate the patient's postoperative status. The information gathered from the telephone interview will be entered into their medical record. If the medical staff person has any concern regarding a patient's postoperative status, the patient will be called by one of the Urogynecology physicians and/or a clinic visit will be scheduled immediately, as is standard practice for patients who are called postoperatively. If the patient requests a postoperative appointment in the clinic, this will also be scheduled immediately. This process is already a standard practice for patient phone calls to our clinic.

In addition to evaluating the patient's postoperative status, the *Patient Cost Survey* will evaluate primary care and emergency room visits, new prescriptions, hospital admissions, estimated travel time, and nonmedical costs.

After the 3 month phone call, each patient will return to the Urogynecology office and meet with a research assistant for a research visit. The patient will then complete the following questionnaires: PFDI-20, EQ-5D, Surgical Pain Scales, and the Postoperative S-CAHPS questionnaire.

Patients randomized to clinic visits:

Patients will be scheduled to receive clinic visits with a physician at the Urogynecology office at 1-2 weeks, 6 weeks, and 3 months. The same scripted interview (See forms: *1-2 Week Interview, 6 Week Interview, and 3 Month Interview*) will be obtained to evaluate the patient's postoperative status. This clinical encounter will also be entered into the medical record. The *Patient Cost Survey* will be completed by the patient at each postoperative visit as well.

Outpatient Visits versus Telephone Interviews for Postoperative Care: A Randomized Controlled Trial (OPTIONS)

These patients will have physical exams performed. The *Adverse Events Physical Exam* form will be completed by the physician performing the postoperative exam.

After the 3 month clinic visit, the patients will meet with the research assistant for a research visit. At this time, the PFDI-20, the EQ-5D, the Surgical Pain Scales, and the Postoperative S-CAHPS questionnaire will be administered. After completion, the patient will be compensated \$50.

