The compensation of study subjects will be prorated. Prior to discharge home, the patient will be compensated \$20. After the 3 month encounter, \$30 will be compensated. These payments will be provided as gift cards. The clinic visits are the standard of care for our postoperative patients. Therefore, these visits will not be compensated. In addition, the telephone calls are the intervention to determine the value of postoperative clinic visits. These telephone calls will not be compensated, because that would require the patient to return to the office which would defeat the purpose of the study.

24. Compensation for Research-Related Injury

Outpatient Visits versus Telephone Interviews for Postoperative Care: A Randomized Controlled Trial (OPTIONS)

If participants are injured or become sick as a result of this study, UNMHSC will provide emergency treatment at the study participants' cost. No commitment is made by the University of New Mexico Health Sciences Center to provide free medical care or money for injuries to participants of the study. Reimbursement for treatment for all related costs of care will be sought from the participant insurer, managed care plan, or other benefits program. The participant will be responsible for any associated co-payments or deductibles required by the insurance. Participants will be encouraged to report any illness or injury they believe to be related to the study to the investigator or research staff. Participants will be given telephone contact information for the Urogynecology office for the purpose of asking any questions or stating any concerns about the study or treatment as a research subject. They may also be directed toward the HRPO. This language will be stated in the written consent document, and reviewed during the informed consent process. Again, the patient undergoes an informed consent process for the surgical procedure regardless of enrollment in the study; hence, there is no additional risks to participate in this study.

25. Consent Process

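### The telephone arm answers the primary 3-month S-CAHPS only after a research-only office trip, so the collection of the primary endpoint differs between arms

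*Combined protocol and SAP*

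**What the plan says.** Section 12 (Study Procedures) describes the end of follow-up separately for each arm.

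- **Telephone arm:** once the 3-month call is done, "each patient will return to the Urogynecology office and meet with a research assistant" for a research visit. At that visit, "The patient will then complete the following questionnaires: PFDI-20, EQ-5D, Surgical Pain Scales, and the Postoperative S-CAHPS questionnaire".
- **Clinic arm:** "After the 3 month clinic visit, the patients will meet with the research assistant for a research visit", where the same four instruments are given.

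No telephone, postal or electronic route is offered for the 3-month S-CAHPS in either arm. The interval between the 3-month contact and the research visit is not stated.

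Section 1.1 makes the primary aim satisfaction at 3 months on the S-CAHPS postoperative domain. Sections 5.3 and 13 name the surgeon rating as the primary outcome. On either definition the data come from this one questionnaire.

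Section 2.2 reports that "patients travel 42.4 miles on average (SD +/- 91.5 miles) for their appointments". Sections 5.3 and 13 expect 10% loss to follow-up, as a single figure. Multiple imputation appears only in the cost-effectiveness part of section 13.

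Section 23 explains that the calls are not paid for, "because that would require the patient to return to the office which would defeat the purpose of the study".

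**The concern.** The trial asks whether calls can replace visits. By the stated route, every telephone-arm woman who supplies primary data has first made an office trip. The women analysed are therefore not a group spared all travel, and they give their rating in the setting that the intervention was meant to remove.

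The reason for the trip also differs. A clinic-arm woman comes for care and answers the survey afterwards; a telephone-arm woman has completed her care and comes only for research. If that makes her less likely to attend, primary data will be lost unequally. If the women who stay away are also the less satisfied ones, an analysis of those who answered would make telephone follow-up look better than it is. In a non-inferiority trial that error favours the claim being tested.

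**Working it through.** **1. The plan's own sample size.** Inputs from sections 5.3 and 13: top-box rate 90% in both arms, margin 15 points, 80% power, two-sided 90% interval (one-sided 0.05).

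n per arm = (1.645 + 0.842)² × (0.9×0.1 + 0.9×0.1) / 0.15² = 6.18 × 0.18 / 0.0225 = 49.5, rounded up to 50. The stated total of 100 is reproduced, with power 80.4%.

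**2. Does unequal loss damage power?** Power = Φ(0.15/SE − 1.645), with SE = √(0.09/n_clinic + 0.09/n_tel). The splits by arm are assumptions.

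| Loss, clinic / telephone | Power, 60 randomized per arm | Power, 54 per arm (after 10% pre-randomization exclusion) |
|---|---|---|
| 10% / 10% | 83.0% | 79.4% |
| 5% / 15% | 82.9% | 79.3% |
| 5% / 20% | 81.8% | 78.1% |

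Power changes little, so the issue is bias.

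**3. Size of the bias.** Let Lt and Lc be the loss in the telephone and clinic arms, and let g be the top-box rate of women who answer minus that of women lost, taken as equal in both arms. The completer rate in an arm is its true rate plus L × g, so:

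shift toward telephone = (Lt − Lc) × g.

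The documents give neither the split nor g. The values below are assumptions. Both splits keep average loss at the planned 10%. With 90% top-box among those who answer, g of 15 to 40 points means 75% down to 50% among those lost.

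| Loss, telephone / clinic | g = 15 points | g = 40 points |
|---|---|---|
| 15% / 5% | 0.10 × 15 = 1.5 points | 0.10 × 40 = 4.0 points |
| 18% / 2% | 0.16 × 15 = 2.4 points | 0.16 × 40 = 6.4 points |
| 10% / 10% | 0 | 0 |
| 5% / 15% | −1.5 points | −4.0 points |

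**4. Effect on the error rate.** Suppose the truth lies at the margin (clinic 90%, telephone 75%), with 60 randomized per arm and completers only analysed. False non-inferiority should then be about 5%. For 15% / 5% loss and g = 40 points:

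- completer rates: clinic 0.90 + 0.05×0.40 = 0.92; telephone 0.75 + 0.15×0.40 = 0.81; difference 0.11
- SE = √(0.92×0.08/57 + 0.81×0.19/51) = 0.0656
- probability = Φ((0.15 − 0.11)/0.0656 − 1.645) = 15.0%

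| Loss, telephone / clinic | g = 20 | g = 30 | g = 40 |
|---|---|---|---|
| 15% / 5% | 8.8% | 11.5% | 15.0% |
| 20% / 5% | 11.2% | 16.4% | 23.5% |

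The second row assumes average loss of 12.5%, somewhat above plan.

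**The case against.** The strongest defence is that both arms answer in person, with a research assistant, after the 3-month contact. Mode and setting are already equal, and each arm needs one office trip to supply the survey. This stands, and it rules out several stronger readings.

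- **A reader might infer that women who skip the trip are lost only from the telephone arm.** The text does not support this. A clinic-arm woman who misses her 3-month visit also gives no S-CAHPS, and her arm is asked for two earlier trips, which could raise its attrition instead. The travel figure is not specific to an arm.
- **A reader might infer that telephone women receive clinic care before answering.** No physician contact or examination is described at the research visit. What is added is travel and in-person contact. Irritation at the trip could lower telephone ratings, which is conservative for non-inferiority; shared contact could draw the arms together, which is not.
- **A reader might take section 23 as condemning the research visit.** Its sentence explains why the calls are unpaid. The reasoning sits awkwardly beside the required trip, but it is not about that trip.
- **A reader might infer that payment differs by arm.** Section 12 says "After completion, the patient will be compensated" 50 dollars, in the clinic-arm text only. Section 23 gives every patient the same 50 dollars, as 20 before discharge and 30 after the 3-month encounter. The total agrees and only the wording needs reconciling. The 30 dollars may also reduce non-attendance.

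Two further cautions hold. Unequal loss is a risk, not something the documents report. And a completers-only primary analysis is inferred from silence: section 13 states complete-case analysis only for cost-effectiveness.

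The defence does not remove the difference in why the trip is made. That difference follows from the protocol's own procedure and is avoidable.

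**Conclusion.** The point holds as an avoidable asymmetry in how the primary endpoint is collected. Telephone-arm women rate their care after a trip made only for research, whereas clinic-arm women do so after a visit made for care. That the clinic-arm research visit falls on the same trip is the natural reading, though it is not stated. The direct effect of the trip on ratings has no known direction.

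The retention risk can be sized only by assumption: 1.5 to 6.4 points toward telephone for a loss difference of 10 to 16 points and a top-box gap of 15 to 40 points. The shift is zero if losses are equal and reversed if clinic loss is higher. Against a 15-point margin this does not invalidate the trial. It is still enough to raise the false non-inferiority rate at the margin from 5% to roughly 9% to 24% in the cases tabulated. The sample size itself is unaffected.

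**What to change.** Amend section 12 so that both arms complete the 3-month S-CAHPS by one identical remote route, right after the 3-month contact and before any office research visit. Examples are a REDCap link, or a call from a research assistant outside the care team. The call is the simpler option: a reliable phone number is already an inclusion criterion, and section 14 already foresees telephone interviews for study data. Keep the office visit for the PFDI-20, EQ-5D and Surgical Pain Scales. Report S-CAHPS completion by arm. Reconcile the payment sentence in section 12 with section 23.

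The cost is a small amendment using existing research staff and REDCap, with no change in sample size. The mode would differ from the preoperative and discharge surveys, and clinic-arm response may fall slightly because those women would no longer be asked in person. The forms left at the office visit would still be exposed to unequal loss, including the EQ-5D that feeds the QALYs. The missing-data rule for the primary outcome is a separate gap that this change reduces but does not close.

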Patients who meet inclusion criteria will be invited to participate in the study. All patients who agree will give written consent prior to their surgery. All patients will complete baseline questionnaires including the following: Surgical Pain Scales, Pelvic Floor Disorder Inventory (PFDI-20), the Preoperative S-CAHPS questionnaire, and the European Quality of Life-5 Dimensions (EQ-5D). Data collected in addition to the above outcome measures will include *Patient Demographics*: age; self-reported race and ethnicity; primary language, marital status, education, health insurance, annual income estimate, and living arrangements. Also, *Medical/Surgical History*: medical comorbidities; prior surgeries for pelvic floor disorders. The physician's physical exam will include the following: Pop-Q stage, height, weight, and pelvic floor disorder diagnoses. The *Patient Contact* form will be completed for all patients enrolled.

Day of Surgery:

On the day of the patient's surgery, the operation that was decided between the patient and her physician will be performed. Information including the indications for surgery, procedures performed, length of surgery, and any intraoperative adverse events will be collected. This information will be recorded by the surgeon immediately postoperative in the *Surgeons Report* form.

Immediately Postoperative:

The Immediately Postoperative S-CAHPS questionnaire will be completed before discharge. If the patient stays overnight in the hospital after surgery, the S-CAHPS questionnaire will be completed on postoperative day #1. For women

Outpatient Visits versus Telephone Interviews for Postoperative Care: A Randomized Controlled Trial (OPTIONS)

undergoing day surgery the form will be completed in the postoperative holding area.

Randomization:

Computer generated randomization will be assigned by research staff uninvolved with recruitment and will be stored in opaque, sequentially numbered envelopes. On the day of the patient's discharge following surgery, the Urogynecology team will call the research coordinator and the patient will be randomized to either clinic visits or telephone calls for postoperative follow-up. Both the clinic visits and telephone calls will be scheduled with specific dates and times. These intervals are at 1-2 weeks, 6 weeks (+/-2 weeks), and 3 months (+/-3 weeks) as this is our current practice. See table 1.

Patients randomized to telephone calls:

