[figure not shown]

Table 2: Study forms at each interval

	Pre-op	Immediately post-op	Time of Discharge	1-2 weeks post-op	6 weeks post-op	3 months post-op
Demographics	X					
S-CAHPS	X		X			X
EQ-5D	X					X
PFDI-20	X					X
Physical Exam	X					
Surgeons Report		X				
Patient Cost	X			X	X	X

Outpatient Visits versus Telephone Interviews for Postoperative Care: A Randomized Controlled Trial (OPTIONS)

Adverse Events			X	X	X	X
----------------	--	--	---	---	---	---

For Clinic Phone Calls other than the calls scheduled at 1-2 weeks, 6 weeks and 3 months:

At the time of discharge, patients receive the contact information for the Urogynecology clinic and on-call staff for after-hours concerns. These calls may be patients from both arms of this study. The qualified medical staff receiving these calls will have a scripted form (the *Interview form*) to complete and added to the medical record, as is standard practice in our clinics. The number of additional phone calls will be calculated. The medical staff will determine if the treatment plan is sufficient over the phone or if a clinic visit is necessary. This process is already standard practice in the Urogynecology clinic.

If a patient randomized to the telephone calls requires a clinic visit, the *Interview, Patient Cost survey, Adverse Events Physical Exam* forms will be completed.

Outcome Measures:

1. Surgical-Consumer Assessment of Healthcare Providers and Systems (S-CAHPS) survey: The “gold standard” for healthcare quality, developed by the Surgical Quality Alliance including the American college of Surgeons and overseen by the U.S. Agency for Healthcare Research and Quality (AHRQ). Incorporates six composites: information to prepare for surgery, communication before surgery, attentiveness on the day of surgery, information to help recovery, communication after surgery, staff at surgeon’s office and the overall surgeon rating. [19]
2. Adverse Events: Using a Clavien-Dindo scale, a validated measure of the severity of adverse events associated with surgery. [20]
3. European Quality of Life-5 Dimensions (EQ-5D): Preference-based utility index algorithm used to calculate each subject’s utility index and compare change in QALYs between the two treatment groups. [21]

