Risks of enrollment in the study include the risk of breach of confidentiality. We will take every measure to try to ensure the security and confidentiality of participants. Participants will be recruited in a private room and will have ample time to consider whether they want to participate in the study. Also, locked filing cabinets will be used to protect patient consent information and collected data.

Outpatient Visits versus Telephone Interviews for Postoperative Care: A Randomized Controlled Trial (OPTIONS)

The link identifying patients and their study numbers will be also stored in a locked cabinet.

Additionally, each patient who will be offered enrollment will already have agreed to surgery for one or more pelvic floor disorders. There are risks inherent to these surgical procedures including bleeding, risk of infection, injury to surrounding organs, especially if an intraperitoneal surgery is performed (bowel, rectum, bladder, ureters, nerves vessels, vagina, uterus, cervix). We attempt to minimize the possibility of unrecognized injuries by performing cystoscopy with all of these procedures to ensure bladder integrity and to note efflux from each ureteral orifice. If the patient opts for a surgery that involves mesh, she will be made aware of the risks of transvaginal mesh included in the FDA warning (e.g. mesh erosion, pelvic pain, and pain with intercourse). Each patient will be provided with informed consent regarding these risks and offered a blood transfusion in the event of life-threatening blood loss. Giving informed consent for these procedures is our practice's standard of care and will not be altered in the study population.

The risk of not presenting for postoperative checks are small, and include that the patient may have problems that are not recognized by the patient or medical staff during phone calls, and could potentially lead to delay of diagnosis. We believe that these risks are small, as women do not routinely undergo a physical exam at all in person postoperative visits if she does not express having any specific problems. In addition, if concerns are raised during calls, women will be scheduled to be seen in the clinic as is our current practice.

Questionnaires will be provided preoperatively, immediately postoperative, and 3 months postoperatively. There is a risk of patient discomfort with completing these questions.

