At all times throughout the clinical investigation, confidentiality will be observed by all parties involved. All data will be secured against unauthorized access. Privacy and confidentiality of information about each subject will be preserved in study reports and in any publication. Each subject participating in this study will be assigned a unique identifier. An IRB-approved HIPAA authorization is required to be signed. All documents containing personal health information (screening logs, consent documents, data forms) are maintained in locked file cabinets with access available only to research staff and investigators. Data is entered into a password protected system. No individual identifiers are entered into the system. The sole link with personal information is maintained by the research team in locked files with access limited to authorized research staff and investigators. This information is only to be used at the study center.

22. Economic Burden to Subjects

Research Procedures	Number of Samples/Procedures	Responsible Party	
		Study	3 rd Party Payer or Participant
Consent	1		
Preoperative EQ-5D Questionnaire	1		
Demographics Form	1		
Preoperative S-CAHPS Questionnaire	1		
Preoperative PFDI Questionnaire	1		
Preoperative Pain scale	1		
Immediate Postoperative S-CAHPS Questionnaire	1		
Cost Survey at 1-2 weeks, 6 weeks, 3 months	3		
Adverse Events Physical Exam Form at 1-2 weeks, 6 weeks, 3 months	3		
3 Month Postoperative S-CAHPS Questionnaire	1		
3 Month Postoperative Pain Scale	1		
3 Month Postoperative PFDI-20	1		

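### Clinic-arm women are to be examined after surgery and telephone-arm women only if brought in, so adverse-event detection may be unequal; the plan leaves its extent unclear and has no analysis for it

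*Combined protocol and SAP*

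**What the plan says.** Section 12, under the clinic-visit arm, states "These patients will have physical exams performed" and has the examining physician complete the Adverse Events Physical Exam form. It attaches no symptom condition and does not say at which visits.

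For the telephone arm, section 12 provides the same form in one circumstance: "If a patient randomized to the telephone calls requires a clinic visit". Such a visit follows staff concern or the woman's own wish ("If the patient requests a postoperative appointment in the clinic, this will also be scheduled immediately"). After the 3-month call "each patient will return to the Urogynecology office and meet with a research assistant for a research visit"; questionnaires are described there and no exam.

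Section 18 calls the risk of problems going unrecognised by telephone small, and gives as a reason that "women do not routinely undergo a physical exam at all in person postoperative visits if she does not express having any specific problems".

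Two tables touch on the matter without settling it. In "Table 2: Study forms at each interval", the Physical Exam row is marked pre-operatively only. This fits the baseline assessment in section 12, where the physician's "physical exam will include the following: Pop-Q stage, height, weight, and pelvic floor disorder diagnoses". The separate Adverse Events row does not say whether the exam form is meant. Section 22 lists "Adverse Events Physical Exam Form at 1-2 weeks, 6 weeks, 3 months" and names no arm.

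Adverse events are one of three components of the primary safety endpoint (section 7.2), under the hypothesis in section 1.1 that they will not differ. Section 13 gives general tests and regression for baseline differences. It contains no analysis by how an event was found.

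**The concern.** A comparison of adverse events is fair only if both arms are searched in comparable ways. If a physician examines complaint-free women in one arm, signs without symptoms will be found there. In the other arm the same signs are found later or not at all. The recorded difference then favours telephone care even when true rates are equal.

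The direction matters because the stated hypothesis is no difference. Under-detection in the telephone arm supports that hypothesis, and could hide the harm section 18 itself names: problems missed by telephone and diagnosed late. The section 18 sentence is also part of the protocol's safety rationale, so its uneasy fit with section 12 is more than a matter of wording.

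**Working it through.** **Plan's own figure.** None exists for adverse events: no rate, margin or sample size. The one stated sample size, 100 in total for satisfaction, reproduces: (1.645 + 0.842)² × 2 × 0.9 × 0.1 / 0.15² = 49.5, so 50 per arm. It does not bear on this point.

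**Routes to detection, side by side.**

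| Route | Clinic arm | Telephone arm |
|---|---|---|
| Same scripted interview (section 12) | at physician visits | by telephone, medical staff |
| Adverse event forms, chart review, outside records (section 14) | yes | yes |
| Exam after a complaint or concern | yes | yes, at a triggered visit |
| Exam without a complaint | yes by section 12; unclear after section 18 | none described |

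Only the last row differs in kind.

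**Model.** All inputs are assumptions. Let p be the true 3-month event rate in both arms, e the share of events found only on a scheduled exam in the clinic arm, and s the share of those that surface by another route in the telephone arm. Interview yield is taken as equal in both arms.

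- All events: clinic p; telephone p − p·e·(1 − s). Bias, telephone minus clinic, is −p·e·(1 − s).
- Without scheduled-exam-only events: clinic p·(1 − e); telephone unchanged. Bias is +p·e·s.
- The gap between the two results is p·e, which does not identify s.

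**Results at p = 20%, e = 20% (p·e = 4 points).**

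| s | All events | Restricted |
|---|---|---|
| 0 | −4 | 0 |
| 0.5 | −2 | +2 |
| 1 | 0 | +4 |

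If exams take place at some visits only, e is smaller; at e = 10% the all-events bias is 0 to −2 points. If they occur only on complaint, e is near 0 and so is the bias. Over p from 10% to 30%, e from 0 to 1/3 and s from 0 to 1, the range is 0 to −10 points. The −10 requires the extreme of all three inputs.

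**Against the trial's precision.** The plan's two 10% losses leave 120 × 0.9 × 0.9 / 2 = 48.6, taken as 49 per arm. The 95% half-width at 20% is 1.96 × √(2 × 0.2 × 0.8 / 49) = 0.158. Exact enumeration of the two-sided Fisher test at 0.05, 49 per arm:

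| Observed rates, clinic / telephone | Significant, favouring telephone | Telephone rate at or below clinic |
|---|---|---|
| 20% / 20% | 1.4% | 55% |
| 20% / 18% | 2.5% | 65% |
| 20% / 16% | 4.3% | 74% |

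**Masking.** Suppose the true rates are 20% clinic and 30% telephone, with e = 20% and s = 0. Telephone is observed at 0.30 × 0.80 = 24%. The true difference is +10; all events show 24 − 20 = +4; the restricted comparison shows 24 − 16 = +8. Both are too low. Telephone looks no worse in 36% of trials (all events) and 19% (restricted), against 15% with equal detection.

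**Precision of the route table.** An exam-only rate of 4 points is 0.04 × 49, about 2 women; for 2 of 49 the exact 95% interval is 0.5% to 14.0%.

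**The case against.** Sections 12 and 18 can be read together. Section 18 may mean not at every visit, and section 12 does not claim every visit. Section 18 also describes usual practice in a risk discussion, whereas section 12 sets trial procedure. This stands as far as it goes: the two sections need not contradict each other. It still leaves open whether and when a complaint-free woman is examined.

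A reader might infer that four places in the protocol disagree. They do not. Table 2's exam row fits the baseline assessment. Section 22 fits section 12, and its silence on arm is no contradiction. The tension is between sections 12 and 18.

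The safeguards are substantial: a shared script, adverse event forms at each encounter, chart review, outside records, and telephone-arm women being asked at each interval whether they want a visit. These narrow the gap for symptomatic or medically attended events. They cannot recover a sign that nobody looks for.

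A reader might also infer that no information on detection route is collected. That cannot be confirmed, because the forms are named but not reproduced. The separate exam form, together with the visit day that section 16 puts on every sheet, may allow partial reconstruction.

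Finally, the added analysis is modest. It does not measure the bias, rests on few events, and assumes that a telephone interview by staff yields as much as one at a physician visit. This is accepted, and is why it is proposed as a sensitivity comparison only.

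**Conclusion.** The concern holds in conditional form. To the extent complaint-free clinic-arm women are examined, adverse-event detection is unequal and the comparison leans toward telephone care. The lean is smaller if exams occur at some visits only, and near zero if they occur only on complaint. The documents do not support saying that the comparison is certainly biased.

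At the assumed 20% rate and 20% exam-only share, the shift is 0 to −4 points, well inside a half-width of about 16. It would rarely produce a significant result on its own. Its main effect is on the estimate, and on how readily the result appears to support no difference. The size rests entirely on assumed rates and shares. The direction rests on section 12 as written and on equal interview yield. The primary satisfaction endpoint is not affected. The change is worth making because it is cheap and the endpoint concerned is the primary safety one.

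**What to change.** 1. Reconcile sections 12 and 18 on postoperative examinations, and state in Table 2 and section 22 which arm and which visits the exam form applies to. This review takes no position on which text is right.
2. Code each adverse event by how it was first found: interview, patient-initiated contact, chart or outside record, triggered exam, or scheduled exam only. An event that is in the chart only because of a scheduled exam belongs in the last category. If the existing forms allow it, a written derivation rule can replace a new field.
3. Keep the all-events comparison. Tabulate scheduled-exam-only events by Clavien-Dindo grade, and add one sensitivity comparison without them. Report each comparison as a risk difference with 95% confidence interval.

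The cost is wording, one field or rule, and one extra comparison, with no added exams, visits or staff. The report should state the limits. The restricted comparison has fewer events and assumes equal interview yield. It can err the other way when exam-only events surface by other routes in the telephone arm. The two results need not bracket the true difference, and problems missed by telephone remain unobserved.
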